6.9.2. Data Safety Monitoring Board (DSMB)

The Coronavirus Disease 2019 (COVID-19) Vaccine Data and Safety Monitoring Board (DSMB) will monitor all randomized COVID-19 vaccine studies supported by the United States Government (USG). The independent DSMB will periodically review blinded and unblinded data of mRNA-1273-P301, including

- continuous monitoring for potential vaccine harm and non-efficacy based on imbalance between mRNA-1273 vs. placebo for both COVID-19 and severe COVID-19 case counts.
- regular review of safety data at scheduled data review meetings
- review the two planned interim analyses

The statistical considerations and methods for DSMB is documented in the Analysis Plan for DSMB (current version: Version 2.0 dated 07-August-2020).

6.9.2.1.Potential Vaccine Harm

The DSMB has continuously monitored potential vaccine harm in this study. Potential vaccine harm is assessed based on imbalance between mRNA-1273 vs. placebo for both COVID-19 and severe COVID-19 case counts using the Safety Set. For harm monitoring, subjects are analyzed according to the IP that they actually received regardless of the group to which they were randomized. For harm monitoring, cases are counted starting after the first dose of study vaccination.

Cases of COVID-19 for the harm monitoring are defined as for the primary efficacy endpoint (eligible symptoms with positive RT-PCR result) but are based on the Safety Set rather than the PPS. For harm monitoring, cases of COVID-19 are derived based on RT-PCR results and symptoms collected in the clinical database to facilitate continuous monitoring.

Details of harm monitoring are provided in the analysis plan for DSMB. The monitoring for potential harm based on COVID-19 would continue to the first interim analysis, and the DSMB can decide how to continue; the harm monitoring for potential harm based on the number of severe COVID-19 cases would continue at least until the primary analysis.

DSMB recommended discontinuation of the harm monitoring reports to the DSMB after the DSMB review meeting on 29-Jan-2021. Thus, harm monitoring is considered completed and discontinued per DSMB recommendation effective immediately.

7. Changes from Planned Analyses in Protocol

Not applicable.

8. References

9.1. Appendix A Standards for Variable Display in TFLs

Continuous Variables: The precision for continuous variables will be based on the precision of the data itself. The mean and median will be presented to one more significant figure than the original results; the SD will be presented to two more significant figures than the original results; the minimum and maximum will be presented to the same precision as the original results.

Categorical Variables: Percentages will be presented to 1 decimal place. If the count is 0, the percentage will not be displayed. If the count equals the denominator, the percentage will be displayed as 100.

9.2. Appendix B Analysis Visit Windows

Analysis will be summarized using the following analysis visit window for post injection assessments:

Step 1: If the assessments are collected at a scheduled visit, the collected data will be mapped to the nominal scheduled visit.

Step 2: If the assessments are collected at an unscheduled visit, the collected data will be mapped using the analysis visit windows described in Table 10 below. For subjects with confirmed COVID-19, unscheduled assessments will be preferably mapped to the visits with respect to the confirmation of COVID-19 (i.e. Illness Visit Day xx) over nominal scheduled visits (i.e. Day xx).

If a subject has multiple assessments within the same analysis visit, the following rule will be used:

- If multiple assessments occur within a given analysis visit, the assessment closest to the target study day will be used.
- If there are 2 or more assessments equal distance to the target study day, the last assessment will be used.

Table 10: Analysis Visit Windows

Visit	Target Study Day	Visit Window in Study Day
Nasopharyngeal swab (or saliva)		
Day 1	1 (Date of First Injection)	1, Pre-first-dose
Day 29	29 (Date of Second Injection)	
Illness Visit Day 1	X (Date of NP Swab test)	X
Illness Visit Day 3	X+2	[X+1, X+2]

Illness Visit Day 5	X+4	[X+3, X+4]
Illness Visit Day 7	X+6	[X+5, X+6]
Illness Visit Day 9	X+8	[X+7, X+10]
Illness Visit Day 14	X+13	[X+11, X+16]
Illness Visit Day 21	X+20	[X+17, X+23]
Illness Visit Day 28	X+27	[X+24, X+34]
Vital Signs		
Day 1	1 (Date of First Injection)	1, Pre-first-dose
Day 1	1 (Date of First Injection)	1, Post-first-dose
Day 29	29 (Date of Second Injection)	[2, 43] Pre-second-dose
Day 29	29 (Date of Second Injection)	[2, 43] Post-second-dose
Day 57	57	[44, 133]
Day 209	209	[134, 301]
Day 394	394	[302, 576]
Day 759	759	[577, 773]
Illness Visit Day 1	X (Date of COVID-19 Confirmation)	X
Illness Visit Day 28	X+27	[X+2, X+34]
Immunogenicity		
Day 1	1	1, Pre-first-dose
Day 29	29 (Date of Second Injection)	[2, 43] Pre-second-dose

Day 57	57	[44, 133]
Day 209	209	[134, 301]
Day 394	394	[302, 576]
Day 759	759	[577, 773]
Illness Visit Day 1	X (Date of NP Swab test)	X
Illness Visit Day 28	X+27	[X+2, X+34]

9.3. Appendix C Imputation Rules for Missing Dates of Prior/Concomitant Medications and Non-Study Vaccinations

Imputation rules for missing or partial start/stop dates of medication are defined below:

1. Missing or partial medication start date:
 - If only Day is missing, use the first day of the month, unless:
 - The medication end date is on/after the date of first injection or is missing/partial AND the start month and year of the medication coincide with the start month and year of the first injection. In this case, use the date of first injection.
 - If Day and Month are both missing, use the first day of the year, unless:
 - The medication end date is on/after the date of first injection or is missing/partial AND the start year of the medication coincide with the start year of the first injection. In this case, use the date of first injection.
 - If Day, Month, and Year are all missing, the date will not be imputed, but the medication will be treated as though it began prior to the first injection for purposes of determining if status as prior or concomitant.
2. Missing or partial medication stop date:

- a. If only Day is missing, use the earliest date of (last day of the month, study completion, discontinuation from the study, or death).
- b. If Day and Month are both missing, use the earliest date of (last day of the year, study completion, discontinuation from the study, or death).
- c. If Day, Month, and Year are all missing, the date will not be imputed, but the medication will be flagged as a continuing medication.

In summary, the prior, concomitant or post categorization of medications and non-study vaccinations is described in the table below.

Table 11: Prior, Concomitant, and Post Categorization of Medications and Non-study Vaccinations

	Medication Stop Date		
	< First Injection Date of IP	≥ First Injection Date and ≤ 28 Days After Last Injection	> 28 Days After Last Injection [2]
Medication Start Date			
< First injection date of IP [1]	P	P, C	P, C, A
≥ First injection date and ≤ 28 days after last injection	-	C	C, A
> 28 days after last injection	-	-	A

A: Post; C: Concomitant; P: Prior

[1] includes medications with completely missing start date

[2] includes medications with completely missing end date

9.4. Appendix D Imputation Rules for Missing Dates of AEs

Imputation rules for missing or partial start dates and stop dates of AEs are defined below:

1. Missing or partial start date:

- If only Day is missing, use the first day of the month, unless:
 - The AE end date is on/after the date of first injection or is missing/partial AND the start month and year of the AE coincide with the start month and year of the first injection. In this case, use the date and time of first injection, even if AE time was collected.

- If Day and Month are both missing, use the first day of the year, unless:
 - The AE end date is on/after the date of first injection or is missing/partial AND the start year of the AE coincides with the start year of the first injection. In this case, use the date and time of first injection, when time is available.
- If Day, Month, and Year are all missing, the date will not be imputed. However, if the AE end date is prior to the date of first injection, then the AE will be considered a pre-treatment AE. Otherwise, the AE will be considered treatment-emergent.

2. Missing or partial end dates will not be imputed.

9.5. Appendix E Schedule of Events

Please refer to Table 16, 17, 18 and 19 in Appendix 1 Schedule of Events in the protocol.

9.6. Appendix F Estimands and Estimand Specifications

Table 12: Intercurrent Event Types

Label	Intercurrent Event Type	Comment
IcEv1 (early discontinuation or death without confirmation of cases, ie, unrelated death)	Early discontinuation from study preventing from confirmation of COVID-19, ie, unrelated death or withdrawal consent prior to documented confirmed COVID-19	Participants in PP Set who withdraw consent or die due to unrelated to COVID-19 without confirmation of being a case will all be included in primary efficacy analysis.
IcEv2 (early COVID-19)	COVID-19 starting up to 14 days after the second dose of IP	Participants in PP Set who experience an early COVID-19 up to 14 days after the second dose of IP will all be included in primary efficacy analysis.

10. Abbreviation: IcEv: intercurrent event, PP: per protocol.

Table 13: Primary Objective and Estimands with Rationale for Strategies to Address Intercurrent Events for Per Protocol Analysis

Objective: To demonstrate the efficacy of mRNA-1273 to prevent COVID-19	
Estimand Description	Vaccine efficacy will be measured using 1 – HR (mRNA-1273/Placebo) of COVID-19 from 14 days after second dose of IP in adults. A hypothetical strategy will be used for early discontinuation (eg, withdrawal consent, deaths unrelated to COVID-19) or early COVID-19 in participants in PP Set..
Target Population	Adults aged 18 years and older in circumstances at a high risk of SARS-CoV-2 infection but without medical conditions that pose additional risk of developing severe disease. The population excludes those previously infected or vaccinated for SARS-CoV-2 or with a medical condition, on treatment that poses additional risks (including those requiring immunosuppressants or immune-modifying drugs), or pre-seropositive.
Variable/Endpoint	Time to COVID-19 disease, censoring at early discontinuation, early COVID-19, or last assessment for an event not being observed, whichever comes earlier.
Treatment Condition(s)	Test: mRNA-1273 Reference: Placebo
Estimand Label	Estimand 1
Population-Level Summary	Vaccine efficacy defined as 1 - HR of mRNA-1273/Placebo
Intercurrent Event Strategy	
IcEv1 (Early discontinuation):	Hypothetical
IcEv2 (early COVID-19):	Hypothetical

Objective: To demonstrate the efficacy of mRNA-1273 to prevent COVID-19

**Rationale for
Strategy(s)**

DHHS	Department of Health and Human Services
ECMO	extracorporeal membrane oxygenation
eCRF	electronic case report form
eDiary	electronic diary
ELISA	enzyme-linked immunosorbent assay
EUA	Emergency Use Authorization
FAS	full analysis set

Abbreviation	Definition
GM	geometric mean
GMFR	geometric mean fold rise
GMR	geometric mean ratio
GMT	geometric mean titer
HIV	human immunodeficiency virus
HR	hazard ratio
ICH	International Council for Harmonisation
IP	investigational product
IRT	interactive response technology
LOD	limit of detection
LLOQ	lower limit of quantification
MAAEs	medically-attended adverse events
MedDRA	Medical Dictionary for Regulatory Activities
MMRM	Mixed Model for Repeated Measures
mRNA	messenger ribonucleic acid
MSD	Meso scale discovery
nAb	neutralizing antibody
NIAID	National Institute of Allergy and Infectious Diseases
NP	nasopharyngeal
OL	open label
PDV	Participant decision visit
PH	proportional hazard
PP	per-protocol
PS	primary series
PT	preferred term
RCDF	reverse cumulative distribution function
REML	restricted (or residual, or reduced) maximum likelihood

Abbreviation	Definition
RT-PCR	reverse transcription polymerase chain reaction
SAE	serious adverse event
SAP	statistical analysis plan
SARS-CoV-2	severe acute respiratory syndrome coronavirus 2
SAS	Statistical Analysis System
SD	standard deviation
SOC	system organ class
SRR	seroresponse rate
TEAE	treatment-emergent adverse event
ULOQ	upper limit of quantification
VE	vaccine efficacy
WHO	World Health Organization
WHODD	World Health Organization drug dictionary

1. Introduction

This statistical analysis plan (SAP) for Part B and Part C, version 2.0, is the amendment of version 1.0, which is based on clinical study protocol (CSP) Amendment 10, dated 07-APR-2022 and the approved electronic case report form (eCRF) Version 16.007. Part B, the Open-Label (OL) Observational Phase of the study, is prompted by the authorization of a coronavirus disease 2019 (COVID-19) vaccine under Emergency Use Authorization (EUA). The CSP Amendment 6 informed all ongoing study participants of the availability and eligibility criteria of any COVID-19 vaccine made available under an EUA and offers participants who originally received placebo in this study the potential benefit of vaccination against COVID-19, given that the primary efficacy endpoint for messenger ribonucleic acid (mRNA)-1273 against COVID-19 was met per the protocol-defined interim analysis. Part C, the Booster Dose (BD) Phase of the study, is prompted by interim results of an ongoing Moderna Phase 2a study (mRNA-1273-P201) that demonstrated enhanced immune responses compared to pre-boost levels and met the noninferiority criteria outlined for booster approval. The CSP Amendment 9 provides the option for a BD to all eligible participants enrolled in Part B.

SAP, Version 1.0 (dated 08 Sep 2020) and Version 2.0 (dated 08 Mar 2021) were developed. For the randomized blinded phase (Part A), three analyses have been performed with Vaccine efficacy assessed:

- an IA of efficacy met the primary objective of efficacy based on the formal pre-specified study success criterion based on a data snapshot on 11 November 2020,
- the primary analysis based on a data snapshot on 25 Nov 2020, and the final analysis of blinded phase/Part A based on database lock on 04 May 2021 with a data cutoff date of 26 March 2021.
- the final analysis of blinded phase/Part A based on database lock of 04 May 2021

The primary objective of VE of mRNA-1273 to prevent COVID-19 has been met at the interim analysis based on a total of 95 adjudicated COVID-19 starting 14 days after the

Dose 2 using the Per-Protocol Set with an VE of 94.5% (95% CI: 86.5, 97.8); $p < 0.0001$ (data snapshot on 25 Nov 2020).

A clinical study report (CSR) has been developed based on the final analysis of the randomized blinded phase (Part A) dated 03 August 2021. Efficacy, safety and immunogenicity of Part A have been analyzed and reported in the CSR for Part A. A CSR addendum presenting safety and efficacy results of the Part B Open-label phase was developed based on the database lock on 04 May 2021.

Therefore, analyses of blinded phase (Part A) data are considered to be completed.

This SAP Part B and Part C focuses on the OL phase and BD phase of the study and provides statistical analysis details/data derivations focusing on Part B and Part C. The SAP Part B and Part C will also provide more details for the unblinded phase (Part B) analyses that were briefly described in SAP Version 2.0, dated 08-MAR-2021. In addition, methods for analysis of the primary series based on Part B and Part A, and for mRNA-1273 using data across parts is included.

Modifications or additions to the analysis plan which are not “principal” in nature is also documented, if the methods in this SAP Part B and Part C differ from the methods described in the protocol, the SAP will prevail.

PPD Biostatistics and programming team, designee of Moderna Biostatistics and Programming department, will perform the statistical analysis; Statistical Analysis System (SAS) Version 9.4 or higher will be used, and R or RStudio may be used.

In this document, subject and participant are used interchangeably; injection of IP, injection, and dose are used interchangeably; vaccination group and treatment group are used interchangeably; Part A and the blinded phase are used interchangeably; Part B and the Open-label (OL) phase are used interchangeably; Part C and the booster dose (BD) phase are used interchangeably; treatment groups and treatment cohorts are used interchangeably; titers and levels are used interchangeably.

2. Study Objectives

2.1. Primary Objectives

Refer to Protocol Section 3 and SAP Part A v2.0. The primary objective of VE of mRNA-1273 to prevent COVID-19 has been met at the interim analysis based on a total of 95 adjudicated COVID-19 starting 14 days after the Dose 2 using the Per-Protocol Set with an VE of 94.5% (95% CI: 86.5, 97.8); $p < 0.0001$ (data snapshot on 25 Nov 2020).

For the blinded phase (Part A), three analyses have been performed with Vaccine efficacy assessed: an IA of efficacy met the primary objective of efficacy based on the formal pre-specified study success criterion, the primary analysis based on a data snapshot on 25 Nov 2020, and the final analysis of blinded phase/Part A based on database lock of 04 May 2021. A clinical study report (CSR) has been developed based on the final analysis of the randomized blinded phase (Part A) dated 03 August 2021.

2.2. Secondary Objectives

2.2.1. Secondary Efficacy Objectives

Refer to protocol Section 3 and SAP version 2.0 for Part A and Part B.

The secondary objective for Part C is to infer effectiveness of the 50 µg of mRNA-1273 booster by establishing noninferiority of Ab response after the booster dose compared to the primary series of mRNA-1273 using GMT values of serum Ab and seroresponse rate (SRR) of post booster in Part C compared with primary series recipients of mRNA-1273.

2.3. Exploratory Objectives

Refer to SAP version 2.0 for the exploratory objectives for Part A and Part B.

The exploratory objectives for Part C are:

- To evaluate the safety of a booster dose of mRNA-1273.
- To evaluate the immunogenicity of a booster dose of mRNA-1273.

3. Study Endpoints

3.1. Primary Endpoints

3.1.1. Primary Efficacy Endpoint (Part A: Blinded Phase Only)

The primary efficacy objective will be evaluated by the VE of mRNA-1273 to prevent the first occurrence of COVID-19 starting 14 days after the second dose of IP, where COVID-19 is defined as symptomatic disease based on the following criteria:

- The participant must have experienced at least TWO of the following systemic symptoms: Fever ($\geq 38^{\circ}\text{C}$), chills, myalgia, headache, sore throat, new olfactory and taste disorder(s), OR
- The participant must have experienced at least ONE of the following respiratory signs/symptoms: cough, shortness of breath or difficulty breathing, OR clinical or radiographical evidence of pneumonia; AND
- The participant must have at least one nasopharyngeal (NP) swab or saliva sample (or respiratory sample, if hospitalized) positive for SARS-CoV-2 by RT-PCR.

3.1.2. Safety Endpoints for Primary Safety Objective

The primary safety objective will be evaluated by the following safety endpoints:

- Solicited local and systemic adverse reactions (ARs) through 7 days after each dose of IP (Part A: Blinded Phase only).
- Unsolicited adverse events (AEs) through 28 days after each dose of IP (Part A: Blinded Phase only).
- Medically-attended AEs (MAAEs) or AEs leading to withdrawal through the entire study period.
- Serious AEs (SAEs) throughout the entire study period.

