3. OBJECTIVES AND ENDPOINTS

Table 1: Objectives and Endpoints

Objectives and Endpoints	
Primary Objective	Primary Endpoints

Efficacy Objective (Primary): To demonstrate the efficacy of mRNA-1273 to prevent COVID-19.
	
Efficacy Endpoints (Primary): Vaccine efficacy of mRNA-1273 to prevent the first occurrence of COVID-19 starting 14 days after the second dose of IP, where COVID-19 is defined as symptomatic disease based on the following criteria:
 
 • The participant must have experienced at least TWO of the following systemic symptoms: fever ($\geq 38^{\circ}\text{C}$), chills, myalgia, headache, sore throat, new olfactory and taste disorder(s), OR • The participant must have experienced at least ONE of the following respiratory signs/symptoms: cough, shortness of breath or difficulty breathing, OR clinical or radiographical evidence of pneumonia; AND • The participant must have at least 1 NP swab or saliva sample (or respiratory sample, if hospitalized) positive for SARS-CoV-2 by RT-PCR

Safety Objective (Primary): To evaluate the safety and reactogenicity of 2 injections of the mRNA-1273 vaccine given 28 days apart.
	
Safety Endpoint (Primary):
 
 • Solicited local and systemic ARs through 7 days after each dose of IP (Part A). • Unsolicited AEs through 28 days after each dose of IP (Part A [all participants] and Part C [only those who receive the BD]). • MAAEs or AEs leading to withdrawal through the entire study period. • SAEs throughout the entire study period.

Objectives and Endpoints	
Efficacy Objectives (Secondary)	Efficacy Endpoints (Secondary)

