8.2. Safety Assessments

Safety assessments will include monitoring and recording of the following for each participant:

- Solicited local and systemic ARs ([Section 8.3.5](#)) that occur during the 7 days following each injection (ie, the day of dosing and 6 subsequent days). Solicited ARs will be recorded daily using eDiaries ([Section 8.2.2](#)) (Part A).
- Unsolicited AEs observed or reported during the 28 days following each injection (ie, the day of injection and 27 subsequent days) (Part A [all participants] and Part C [only those

who receive the BD]). Unsolicited AEs are AEs that are not included in the protocol-defined solicited ARs ([Section 8.3.5](#)).

- AEs leading to discontinuation from dosing and/or study participation from Day 1 through Day 759 or withdrawal from the study.
- MAAEs from Day 1 through Day 759 or withdrawal from the study.
- SAEs from Day 1 through Day 759 or withdrawal from the study.
- AEs of special interest (AESIs; for participants who receive the BD in Part C) from BD-Day 1 through Day 759 or withdrawal from the study.
- Abnormal vital sign measurements.
- Physical examination findings.
- Pregnancy and accompanying outcomes.
- Concomitant medications and non-study vaccinations.

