8.3.7. Recording and Follow-up of an AE and/or SAE

The investigator is responsible for ensuring that all AEs and SAEs are recorded in the eCRF and reported to the Sponsor.

Solicited ARs will be collected from Day 1 through 7 days after each dose (Part A). Other (unsolicited) AEs will be collected from Day 1 through 28 days after each dose in Part A (all participants) and Part C (only those who receive the BD).

Both MAAEs and SAEs will be collected from Day 1 throughout the entire study duration (Day 759 for all participants), as specified in the SoEs ([Table 16](#), [Table 17](#), [Table 18](#), [Table 19](#), [Table 21](#), [Table 22](#), and [Table 23](#)). Any AEs occurring before receipt of IP will be analyzed separately from TEAEs.

At every study site visit or telephone contact, participants will be asked a standard question to elicit any medically related changes, including surveillance for COVID-19 symptoms, in their well-being according to the scripts provided. Participants will also be asked if they have been hospitalized, had any accidents, used any new medications, changed concomitant medication regimens (both prescription and over-the-counter medications), or had any non-study vaccinations.

In addition to participant observations, physical examination findings or other documents relevant to participant safety classified as an AE will be documented on the AE page of the eCRF.

After the initial AE/SAE report, the investigator is required to proactively follow each participant at subsequent visits/contacts. All AEs and SAEs will be treated as medically appropriate and followed until resolution, stabilization, the event is otherwise explained, or the participant is LTFU (as defined in [Section 7.4](#)).

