If a subject received any dose of mRNA-1273 at any injection, regardless of the treatment group the subject was randomized to, the subject will be included to mRNA-1273 100 µg group as the actual treatment group received for safety analyses.

All analyses and data summaries/displays for disposition, baseline demographics and characteristics will be provided by Baseline SARS-CoV-2 Status (negative, positive, and overall) and treatment group unless otherwise specified. All analyses and data summaries/display for efficacy will be provided by treatment group using appropriate analysis population unless otherwise specified.

Analysis Periods

The following analysis periods and treatment groups will be used for efficacy analyses for the blinded phase (Part A):

Part A Group	Description	Blinded/Part A Analysis Period for Efficacy
mRNA-1273	Participants randomized to mRNA-1273 in the Blinded Phase	From randomization to earlier date of Participant Decision Visit (PDV)/unblinding, study discontinuation, study completion, death, or data cutoff date for efficacy)
Placebo	Participants randomized to Placebo in the Blinded Phase	

The analysis period and treatment groups of the blinded phase (Part A) for Safety analyses is summarized below:

Part A Group	Description	Blinded/Part A Analysis Period for Safety
--------------	-------------	---

mRNA-1273	Participants received at least one dose of mRNA-1273 in the Blinded Phase	From the first dose of study IP to the earlier date of (study discontinuation, study completion, death, data cutoff for safety, PDV/unblinding) for those who did not receive study IP in Part B. For participants received study IP in Part B, from the first dose of study IP in study to the earlier date of (data cutoff for safety, or 1st dose of study IP in Part B)
Placebo	Participants only received Placebo in the Blinded Phase	

The above analysis period for safety analysis in Part A is also referred to as Overall Period in Part A. For Part A, up to 28 days after any vaccination, starts at the day of each vaccination and continue through the earliest date of (the day of each vaccination and 27 subsequent days, next vaccination [if applicable]), will be used as the primary analysis period for safety analyses including unsolicited AE, except for solicited AR, unless specified otherwise.

Part B

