5.1.5. Analysis Periods

Analysis periods and treatment groups for analysis of Part B, Part C, and Primary Series are summarized in Table 1. For effectiveness, participants will be included in treatment groups based on ‘as-planned’ or ‘intent-to-treat’ assignments; for safety, participants will be included in treatment groups based on ‘as treated’ groups (treatment actually received), details are provided to Appendix F. For analysis of immunogenicity, ‘per-protocol’ sets will be used as analysis population and ‘per-protocol’ sets require participants receiving planned treatments.

Table 1 Analysis Periods for Analyses of Part B, Part C, and Primary Series

Treatment Group/Cohort	Description	Analysis Period
Part B (Effectiveness)		
mRNA-1273	Participants randomized to mRNA-1273 in the Blinded Phase Date of reference: PDV/unblinding	From PDV/unblinding to earlier date of (BD-1 visit, DBL or data cutoff date for efficacy, last observed in study ^a)
Placebo	Participants randomized to Placebo in the Blinded Phase and did not request to receive mRNA-1273 in Part B Date of reference: Dose 1 of mRNA-1273	
Placebo-mRNA-1273	Participants randomized to Placebo in the Blinded phase and requested to receive mRNA-1273 in Part B Date of reference: Dose 1 of mRNA-1273 in Part B	
Part B (Safety)		
mRNA-1273	Participants received at least one dose of mRNA-1273 in the Blinded Phase	From PDV/unblinding or 1 st dose of mRNA-1273 in Part B to earlier date of (BD- Day 1, DBL or data cutoff date for safety, last observed in study ^a).
Placebo	Participants only received Placebo in the Blinded Phase and did not receive mRNA-1273 in Part B	
Placebo-mRNA-1273	Participants only received Placebo in the Blinded phase and received mRNA-1273 in Part B	
Part C (Effectiveness, Immunogenicity, Safety)		
Booster 50 µg after mRNA-1273 primary series	Participants randomized to/received mRNA-1273 in the Blinded Phase and received booster 50 µg in Part C Date of reference: date of booster	From dose date in Part C to earlier date of (DBL or data cutoff date for safety, last observed in study ^a).

Booster 50 µg after Placebo-mRNA-1273 Primary Series	Participants randomized to /only received Placebo in the Blinded Phase and received at least one dose of mRNA-1273 in Part B and received booster 50 µg in Part C Date of reference: date of booster	

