5.4.1. Unsolicited Treatment-emergent Adverse Events

A treatment-emergent AE (TEAE) is defined as any event occurring during the study not present before exposure to the IP or any event already present that worsens after exposure

to study vaccine. Worsening of a pre-existing condition after vaccination will be reported as a new AE.

Adverse events will also be evaluated by the investigator for the coexistence of MAAE which is defined as an AE that leads to an unscheduled visit to a healthcare practitioner.

Unsolicited AEs will be coded by PT and SOC using MedDRA and summarized by vaccination group.

All summary tables (except for the overall summary of AEs) for unsolicited AEs will be presented by SOC and PT or by PT only for TEAEs with counts of subjects included. SOC will be displayed in internationally agreed order.

When summarizing the number and percentage of subjects with an event, subjects with multiple occurrences of the same AE or a continuing AE will be counted once. Only the maximum severity level will be presented in the severity summaries, and the strongest relationship level will be presented in the relationship summaries. Percentages will be based upon the number of subjects in the Safety Set within each treatment cohort.

Unsolicited TEAEs will be summarized for Part B, Part C, and Primary Series using analysis periods as defined in Section 5.1.

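### The Part B/C SAP limits the 28-day unsolicited-AE endpoint to Part A, so neither SAP specifies the 28-day post-booster summary that the protocol lists

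*SAP*

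**What the plan says.** **Protocol.** Table 1 in Section 3 lists, among the primary safety endpoints, "Unsolicited AEs through 28 days after each dose of IP (Part A [all participants] and Part C [only those who receive the BD". Section 8.2 defines the window: "Unsolicited AEs observed or reported during the 28 days following each injection (ie, the day of injection and 27 subsequent days". Section 8.3.7 sets the collection period to match: "Other (unsolicited) AEs will be collected from Day 1 through 28 days after each dose in Part A (all participants) and Part C", the latter limited to booster recipients. Table 23 in Section 11.1 records unsolicited AEs from BD-1 through BD-2 (BD-Day 29) and not at BD-3 (BD-Day 181).

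**Part B/C SAP.** Section 1 says the plan is based on protocol Amendment 10. Section 3.1.2 nevertheless gives the endpoint as "Unsolicited adverse events (AEs) through 28 days after each dose of IP (Part A: Blinded Phase only". For the tables, Section 5.4.1 says: "Unsolicited TEAEs will be summarized for Part B, Part C, and Primary Series using analysis periods as defined in Section 5.1". In Section 5.1.5, Table 1 gives booster recipients one period for effectiveness, immunogenicity and safety: "From dose date in Part C to earlier date of (DBL or data cutoff date for safety, last observed in study". Section 1 adds that the SAP prevails where it differs from the protocol. Section 6, on changes from the protocol's planned analyses, reads as not applicable.

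**Part A SAP (version 2.0).** Section 6.1 does set a 28-day period that "will be used as the primary analysis period for safety analyses including unsolicited AE", but it is introduced by "For Part A, up to 28 days after any vaccination, starts at the day of each vaccination". Section 6.6 says its language pertains to Part A unless specified otherwise.

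**The concern.** The two documents name different study parts for the same endpoint, and the SAP claims precedence without declaring a change. A programmer who followed the Part B/C SAP would tabulate booster AEs over all follow-up and would have no instruction to produce the 28-day summary.

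That matters because collection is not uniform over the longer period. After Day 28, a non-serious AE that is not medically attended, not an AESI and not a reason for withdrawal is no longer collected, while the other categories continue. Protocol Section 8.1.2 makes every confirmed COVID-19 case an MAAE. Section 5.3.1.2.2 of the Part B/C SAP itself treats the time from 01-Dec-2021 as an Omicron wave, so such cases can be expected during booster follow-up. A single percentage over the whole period would reflect reactions close to the dose, later community illness and each person's length of follow-up together, and it would have no counterpart to set beside Part A's primary 28-day table.

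**Working it through.** The plan states no figure to reproduce. The check compares the texts, followed by one ratio.

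**Step 1. Is the 28-day rule for the booster stated anywhere in either SAP?**
- Part B/C SAP Section 3.1.2: the endpoint is restricted to Part A.
- Part B/C SAP Sections 5.4.1 to 5.4.1.3: no 28-day window.
- Part B/C SAP Section 5.1.5, Table 1: one Part C period, with no sub-period.
- Part B/C SAP Appendix C: a 28-day post-dose cut appears, but only to classify concomitant medications.
- Part A SAP Sections 6.1, 6.6 and 6.6.1: a 28-day rule for AEs, confined to Part A.

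So it is stated in neither. Section 3.1.2 of the Part A SAP carries the same Part A restriction. That plan was written to protocol Amendment 6, before Part C existed, so carried-over text is the likely source.

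**Step 2. What enters the planned Part C table?** Collection is taken from Protocol Sections 8.1.2, 8.2 and 8.3.7 and Table 23.

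| Event after the booster | To Day 28 | After Day 28 |
|---|---|---|
| Non-serious, not medically attended, not an AESI, not leading to withdrawal | collected | not collected |
| MAAE, including confirmed COVID-19 | collected | collected |
| SAE, AESI, AE leading to withdrawal | collected | collected |

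The definition of an unsolicited AE in Protocol Section 8.3.1 has no upper time limit, and the overview in Part B/C SAP Section 5.4.1.1 counts medically attended, fatal and discontinuation events among unsolicited events. A late MAAE therefore falls in the any-unsolicited-TEAE row unless a window removes it.

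**Step 3. Effect on the percentage.** Section 5.4.1 uses numbers of subjects as denominators, not person-time. Let p be the proportion of boosted participants with an unsolicited TEAE by Day 28, and let q be the proportion of the remainder who have a first qualifying MAAE, SAE, AESI or withdrawal AE later. Then

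whole-period percentage = p + (1 − p) × q.

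The first term is the protocol's endpoint. The excess, (1 − p) × q, grows with follow-up. The documents give neither p nor q, so I do not put a value on it.

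**Step 4. Ratio of the windows.**
- Protocol window: booster day + 27 days = 28 days.
- SAP period for a completer not cut off by database lock or data cutoff: at least to BD-Day 181. With the ±14-day window in Table 23 this is 181 − 14 = 167 to 181 + 14 = 195 days.
- 181 / 28 = 6.5; 167 / 28 = 6.0; 195 / 28 = 7.0.
- Share of that period with full AE collection: 28 / 181 = 15%.

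These are ratios of observation time. They do not estimate the distortion in any AE rate.

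**The case against.** The best reply is that little is lost. Minor AEs are collected only to Day 28, so for them the planned table already is the 28-day table, and the whole-period table contains every event from the first 28 days. The SOC and PT section (5.4.1.2) lists its tables and then says that several will also be provided. The parallel Part A sentence (Part A SAP Section 6.6.1.2) ends by naming the Overall Stage. The Part B/C sentence has lost its period, which hints at two intended periods and a drafting slip. Booster safety is an exploratory objective, the primary safety objective concerns two injections, Protocol Section 9.5.2.1 states no window for Part C and leaves details to the SAP, and the summaries are descriptive.

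Most of this is correct, but it does not supply the missing period. A likely slip still has to be corrected in a document that overrides the protocol, and the protocol names Part C within the endpoint whatever the rank of the objective. The collection argument fails for the any-event row, because later MAAEs, SAEs, AESIs and withdrawal AEs are added to it.

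Four stronger conclusions might be inferred, and the documents do not support them.
- *That the 28-day result can never be produced.* It is unspecified, but it can be derived from data already collected.
- *That booster AEs cannot be compared with Part A at all.* Part A SAP Sections 6.6.1.1 and 6.6.1.2 also provide unsolicited TEAE tables for the Overall Stage, with the same mixture of collection rules. Only the match to the primary 28-day table is missing.
- *That treatment-related rows are distorted as much as the others.* Protocol Section 8.3.10 requires a reasonable time sequence and the vaccine as the more likely explanation, which late COVID-19 would seldom meet.
- *That follow-up can be dated by calendar.* No passage says when boosting ended, and the April 2022 cutoff in Part B/C SAP Section 5.3.1.2.1 is an example for an efficacy variant period, not a safety cutoff.

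**Conclusion.** The inconsistency is real and should be corrected. The protocol sets a 28-day unsolicited-AE endpoint for booster recipients, and neither SAP specifies it. The row for any unsolicited TEAE would be affected most and the severe row less. No hypothesis test depends on these tables, and no data are lost.

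The factor of about 6.5 (6.0 to 7.0 over the visit window) assumes a participant followed to BD-3 and not truncated by lock or cutoff. An earlier cutoff shortens the period, and follow-up beyond BD-3 lengthens it. How far the percentages would move depends on event rates that the documents do not give. The COVID-19 component assumes that confirmed cases recorded as MAAEs are not removed from the AE tables, and the SAP states no such exclusion.

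**What to change.** 1. In Part B/C SAP Section 3.1.2, replace the Part A restriction on unsolicited AEs with Part A and Part C (booster recipients), to agree with Table 1 of the protocol.
2. In Sections 5.1.5 and 5.4.1, add the booster day and the 27 subsequent days as the primary period for Part C unsolicited TEAE summaries in the Part C Safety Set.
3. Keep the whole-period tables as additional summaries, as Part A does with its Overall Stage, and label each table with its period. The repeated sentence in Section 5.4.1.2 should name the period it refers to.
4. If leaving out the 28-day summary is deliberate, record and justify it in Section 6.

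The cost is SAP wording, one period flag in the analysis dataset and repeat runs of existing table programs. No new data are needed.
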